11. STATISTICAL METHODS

Statistical analysis will be done by the sponsor or under the authority of the sponsor. A general description of the statistical methods to be used to analyze the immunogenicity and safety data is outlined below. Specific details will be provided in the Statistical Analysis Plan.

Planned analyses are described in Section 11.8.

11.1. Analysis Sets

Vaccination assignment will follow the as-treated principle.

^{cc} If within the screening window. Otherwise, rescreening is required.

The Full Analysis (FA) set includes all subjects who were randomized and received at least one dose of study vaccine, regardless of the occurrence of protocol deviations. All safety analyses will be based on the FA set. As a sensitivity analysis, key immunogenicity tables will also be based on the FA set.

The Per-protocol Immunogenicity (PPI) analysis set will include all randomized and vaccinated subjects for whom immunogenicity data are available, excluding subjects with major protocol deviations expected to impact the immunogenicity outcomes. Any subject with an anamnestic response at Day 8 will not be included in the PPI analysis set.

In addition, the following samples will not be included in the PPI set:

- If subjects miss one or more doses, but continue the planned visit schedule, samples taken after the planned but missed dose(s) will not be taken into account;
- For subjects who experience a natural RSV infection (based on RT-PCR, or other sources), samples taken after the natural infection will not be taken into account.

The analysis of immunogenicity will be based on the PPI set.

Additionally, a modified intent-to-treat (mITT) analysis set is defined as a subset of the FA set excluding subjects who are seronegative at screening but for whom there is an anamnestic response at Day 8. The criteria for assessment of the anamnestic response will be specified in the SAP. The mITT set will be the primary analysis set for assessment of RSV infection in seronegative subjects.

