The following analyses will be performed:

- Primary analysis 28 days post-final dose includes safety and immunogenicity; unblinded
- Interim analysis performed when all subjects have data of 1 RSV season post-Dose 1, includes safety and immunogenicity; unblinded
- Final analysis at the end of the study; unblinded

The primary analysis and interim analysis may be combined into one analysis. These analyses will also be shared with the IDMC.

Additional interim analyses (blinded or unblinded) may be performed during the study for the purpose of informing future vaccine-related decisions in a timely manner, or upon health authority request. The results will not influence the conduct of the study in terms of early termination or later safety or immunogenicity endpoint assessments, and will only be available to a selected group of sponsor personnel, excluding sponsor personnel involved in data collection or data management and clinical immunology laboratory personnel.

Immunogenicity Analyses

No formal hypothesis on immunogenicity will be tested. Descriptive statistics (geometric mean and 95% confidence interval for ELISA and virus neutralization assays; median and quartiles for ELISpot and ICS) will be calculated for continuous immunologic parameters at all timepoints. Graphical representations of immunologic parameters will be made as applicable.

Frequency tabulations will be calculated for discrete (qualitative) immunologic parameters as applicable.

RSV Infection

The incidence of any RSV infection, as described above under 'RTI PROCEDURES', in Ad26.RSV.preF and control subjects will be summarized by descriptive statistics.

Safety Analyses

No formal statistical testing of safety data is planned. All safety data will be analyzed descriptively by regimen.

TIME AND EVENTS SCHEDULE

Phase	Screening	----- Vaccination Phase -----													Safety FU ^a
Visit #	1	2	3	4	5	6	7	8	9	10	11	12 ^a	EoS	Exit ^c	FU outside RSV season at 30-day intervals; FU within RSV season at 14-day intervals
Visit Timing		Vac 1	Vac 1 + 3 d	Vac 1 + 7 d	Vac 2 (Vac 1 + 28 d)	Vac 2 + 3 d	Vac 2 + 7 d	Vac 3 (Vac 2 + 28 d)	Vac 3 + 3 d	Vac 3 + 7 d	Vac 3 + 28 d	Vac 3 + 6 mo	End of Season ^b		
Visit Week		0		1	4		5	8		9	12	34			
Target Visit Day ± Window (days)	-42 to 1	1	4±1	8 -1/+3 ^d	29±3	32±1 ^e	36±2 ^{d,e}	57±3 ^e	60±1 ^e	64±2 ^{e,f}	85±3 ^e	239±14 ^e	+28		

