3. STUDY DESIGN AND RATIONALE

3.1. Overview of Study Design

This is a multi-center, randomized, observer-blindⁱ, Phase 1/2a study, to be conducted in 36 male and female RSV-seronegative toddlers aged ≥ 12 to ≤ 24 months.

Each subject's RSV serostatus will be assessed by RSV enzyme immunoassay (EIA) at screening^j (see Section 9.1.3.1). *Note*: serostatus may be assessed via this assay if available from a different study of the sponsor (VAC18194RSV2001). If done within 42 days of first dose, this assessment would not have to be repeated in the absence of a history of respiratory infection during that period. Additionally, the seronegative status will be confirmed by the absence of an anamnestic humoral immune response (which is usually observed 7-10 days post antigen re-exposure in RSV seropositive subjects) from blood samples taken 7 days after the first dose.

ⁱ *Note*: The vaccine administrator will be unblinded but will have no other study function following dosing. The site staff or qualified professional staff who will do the observation and the subjects will be blinded.

^j The cut-off for seronegativity is a titer < 1 EIA unit.

Subjects will be randomized 1:1 to receive either Ad26/Ad26/Ad26 (at 2.5×10^{10} vp) or placebo/placebo/Nimenrix ^{k,1} (or placebo/placebo/placebo) (Table 4).

Table 4: Study Design VAC18194RSV2002

Group	N ^a	Day 1	Day 29/Week 4	Day 57/Week 8
RSV-seronegative toddlers 12 to 24 months				
Group 1	18	Ad26.RSV.preF (2.5×10^{10} vp)	Ad26.RSV.preF (2.5×10^{10} vp)	Ad26.RSV.preF (2.5×10^{10} vp)
Group 2	18	Placebo (saline)	Placebo (saline)	Nimenrix ^b or Placebo (saline)

N = number of subjects; vp = viral particles

^a: At the time of Amendment 6, 37 subjects have been enrolled.

^b: In countries where the commercial vaccine Nimenrix is licensed, placebo (0.9% saline) can be replaced with Nimenrix as the Day 57 vaccination for the study subjects in the control group, in accordance with the local label and local regulations, and unless contra-indicated. Nimenrix will be administered, only if permitted by the subject's parent/legal guardian and following PI assessment on a case-by-case basis as vaccination with Nimenrix outside this study might be preferred (joint parent/legal guardian and PI decision). In the US, Nimenrix will not be used unless it has been licensed for use or an Investigational New Drug (IND) has been submitted.

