5. STUDY VACCINE ALLOCATION AND BLINDING

Study Vaccine Allocation

Central randomization will be implemented in this study. Subjects will be randomly assigned to a treatment group based on a computer-generated randomization schedule prepared before the study by or under the supervision of the sponsor. The randomization will be balanced by using randomly permuted blocks. No stratification will be applied.

The randomization ratio is 1:1.

The interactive web response system (IWRS) will assign a unique code, which will dictate the group assignment for the subject. The requestor must use his or her own user identification and personal identification number when contacting the IWRS, and will then give the relevant subject details to uniquely identify the subject.

If randomized subjects are withdrawn from vaccination before the first dose is administered, additional subjects may be recruited to replace these subjects at the discretion of the sponsor. Any replacement subject will be assigned to the same group as the original (discontinued) subject. The replacement subject's randomization number will equal the randomization number of the discontinued subject +1000 (for example subject 0001 would be replaced by subject 1001). These additional subjects should also be randomized through IWRS.

Any randomized subject who is withdrawn from the study for reasons other than due to an AE after the first dose but before the second dose might be replaced at the discretion of the sponsor. Any replacement subject will be assigned to the same group as the original (discontinued) subject. The replacement subject's randomization number will equal the randomization number of the discontinued subject +2000.

Every effort will be made to determine the serostatus of subjects. During the study, any subject who was assessed as seronegative at screening and who subsequently shows an anamnestic response at Day 8 will be replaced if possible.

Blinding

The investigator will not be provided with randomization codes until the final analysis is performed. The codes will be maintained within the IWRS, which has the functionality to allow the investigator to break the blind for an individual subject.

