RSV seropositivity will be assessed by RSV EIA at screening. The cut-off for seronegativity is a titer <1 EIA unit. *Note*: Serostatus may be assessed via this assay if available from a different study of the sponsor (VAC18194RSV2001). If done within 42 days of first dose, this assessment would not have to be repeated in the absence of a history of respiratory infection during that period. Every effort will be made to determine the serostatus of subjects. Any subject who was assessed as seronegative at screening and who subsequently shows an anamnestic response at Day 8 will be replaced if possible.

The seronegative status will be confirmed by the absence of an anamnestic humoral immune response from blood samples taken 7 days after the first dose. An anamnestic response is defined as a >4-fold increase in pre-F ELISA within 7 days post Dose 1. The criteria for assessment of the anamnestic response will be specified in the SAP.

General eligibility for this clinical study will be dependent on results of the medical assessment. Study subjects who qualify for inclusion based on the medical history and physical examination will be scheduled for enrollment and first vaccination (Visit 2) within 42 days. If necessary, the screening visit may be split into several visits.

After medical history and physical examination data have been reviewed for completeness and adherence to inclusion and exclusion criteria, the subject can be deemed eligible for the study.

The sponsor collects AEs, whether serious or non-serious, related to the study procedures or non-investigational (concomitant) Janssen products from ICF signature onwards. SAEs (and any associated concomitant medications) will be collected from first dose administration until the end of the study. Unsolicited AEs will be recorded on the Adverse Event page of the eCRF from the time of each vaccination through the following 28 days, together with information on any concomitant medications.

Between screening and Day 1, only MA-RTIs (including severe LRTIs) will be collected. Any MA-RTI or severe LRTI which occurs during this period will be recorded on the Medical History page of the eCRF.

9.1.3.2. Vaccination Phase: Day 1 to Day 239

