11.5. Immunogenicity Analyses

No formal hypothesis on immunogenicity will be tested. Descriptive statistics (geometric mean and 95% confidence interval for ELISA and virus neutralization assays; median and quartiles for ELISpot and ICS) will be calculated for continuous immunologic parameters at all timepoints. Graphical representations of immunologic parameters will be made as applicable.

Frequency tabulations will be calculated for discrete (qualitative) immunologic parameters as applicable.

The primary analysis set for immunogenicity is the PPI set. As a sensitivity analysis, key tables will also be based on the FA set. Depending on their occurrence, the effect of missed doses or natural infections might be further explored. Note that they will be included in the tables showing the FA set.

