11.6. RSV Infection

The presence of RSV infection, as described in Section 9.2.2, will be assessed by RT-PCR. The presence of RSV infection will be summarized by descriptive statistics.

Any RTI or otitis media case recorded as an AE in the eCRF that is subsequently found to be RSV positive by RT-PCR (central laboratory or based on CEC assessment if available) will be excluded from the safety analysis and tabulated separately (refer to Section 11.7).

The mITT set is the primary analysis set for assessment of RSV infection in seronegative subjects.

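### RSV infection is assigned only to the mITT set, whose Day 8 exclusion can in practice remove only Ad26 recipients; show the FA set beside it and name FA for the monitoring rule (minor).

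*Protocol*

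**What the plan says.** Protocol 11.1 builds the mITT set from the FA set, "excluding subjects who are seronegative at screening but for whom there is an anamnestic response at Day 8". Section 11.6 repeats the assignment: "The mITT set is the primary analysis set for assessment of RSV infection in seronegative subjects". Section 9.1.3.1 gives the criterion: "An anamnestic response is defined as a >4-fold increase in pre-F ELISA within 7 days post Dose 1". Section 3.1 describes the response as one "which is usually observed 7-10 days post antigen re-exposure in RSV seropositive subjects". By the design table in 3.1, the Day 1 injection is Ad26.RSV.preF in one arm and saline in the other; Nimenrix can replace saline only at Day 57. Section 5 adds that a child seronegative at screening "who subsequently shows an anamnestic response at Day 8 will be replaced if possible".

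RSV infection is described by arm: the Synopsis (Statistical Methods, RSV Infection) says the incidence "in Ad26.RSV.preF and control subjects will be summarized by descriptive statistics".

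An FA counterpart is stated for immunogenicity only, in 11.1 ("As a sensitivity analysis, key immunogenicity tables will also be based on the FA set") and in 11.5 ("As a sensitivity analysis, key tables will also be based on the FA set"). Neither 11.1 nor 11.6 has a matching sentence for RSV infection. The monitoring rule in 11.3.1.3 names no analysis set. The SAP supplied covers the IDMC analyses; it defines only the FA set (2.3.1) and names no set in 5.2, where the RSV tables and confidence limits are described.

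**The concern.** The exclusion happens after randomization and depends on what was injected. Take a child who has already had RSV but was missed by the screening EIA (called primed below). Given Ad26.RSV.preF, the child meets the antigen again and can be removed at Day 8. Given saline, the same child meets no antigen and stays. The Ad26 arm of mITT has thus been screened twice and the control arm once, so the two arms no longer describe the same kind of child. RSV infection rates in the two arms are an exploratory objective, and severe RSV-LRTI is the secondary endpoint used as a preliminary signal of enhanced disease. If primed and naive children differ in risk, part of any difference between arms in mITT comes from the exclusion. With only mITT shown, a reader could not see how much.

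The unnamed set also matters for the monitoring rule, which turns on counts of two to four events.

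**Working it through.** **1. Who can be excluded.** The criterion needs a pre-F rise between baseline and Day 8. The Ad26 arm receives a vector encoding pre-F on Day 1; the control arm receives saline. A control could still qualify through natural infection (the baseline sample may be taken at screening, up to 42 days before dosing) or through assay error. Otherwise only Ad26 recipients can be dropped.

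**2. Effect on the comparison with no vaccine effect.** Let f be the primed share, p0 the naive risk and p1 the primed risk, and assume every primed Ad26 child is detected at Day 8.
- mITT: Ad26 risk = p0; control risk = (1−f)p0 + f·p1.
- FA: both arms = (1−f)p0 + f·p1, so no spurious difference.
- Shift in mITT, in children per arm of 18: 18·f·(p0−p1).

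Neither f, p0 nor p1 is in the documents. With an assumed p0 = 0.50:

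| f (assumed) | p1 = 0 | p1 = 0.25 | p1 = 0.50 |
|---|---|---|---|
| 2% | 18×0.02×0.50 = 0.18 | 0.09 | 0 |
| 10% | 0.90 | 0.45 | 0 |
| 20% | 1.80 | 0.90 | 0 |

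The shift stays below one child when f·|p0−p1| < 1/18 = 0.056. At f = 10% that allows a risk difference of up to 0.56; at 20%, up to 0.28. Incomplete Day 8 detection makes the shift smaller. If primed children had the higher risk, the sign would reverse.

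**3. Can the background figures fix the risk ratio?** Protocol 1.1 cites infection rates of 68.8% in the first year and 82.6% in the second. Taking these at face value, p1 = (0.826 − 0.312·p0)/0.688.
- p0 = 1.00: p1 = 0.747, ratio 0.75.
- p0 = 0.826: p1 = 0.826, ratio 1.00.
- p0 = 0.50: p1 = 0.974, ratio 1.95.

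The ratio lies on either side of 1 depending on a naive risk that is not given. These figures settle neither size nor direction.

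**4. Monitoring rule.** Inputs: 18 per arm; Wilson-score limits for a difference (the Newcombe method cited in the SAP), one-sided. Lower limit = d − √[(pA−lA)² + (uC−pC)²], where d = pA−pC, and lA and uC are the lower Wilson limit for Ad26 and the upper one for control.

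The protocol's own example for 2 versus 0 events reproduces. At one-sided 80%, the Wilson lower limit for 2/18 is 0.0629 and the upper limit for 0/18 is 0.0379. The lower limit is 0.1111 − √[(0.1111−0.0629)² + 0.0379²] = +0.050. The lower 95% limit is −0.039 and the upper 95% limit is 0.286. That is the increased-monitoring tier, as 11.3.1.3 says.

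Now suppose one of those two children was a Day 8 responder and the rule were run on mITT. The count becomes 1/17 versus 0/18. With one event, 11.3.1.3 prescribes no analysis. SAP 5.2 still sets the trigger at 3 events where the protocol has 2; at that trigger, losing one of three cases would likewise prevent the analysis.

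**5. What FA costs.** Assume a true ratio of 2.0 in naive children and 1.0 in primed children, with r = p1/p0 in controls. FA = [2(1−f) + f·r]/[(1−f) + f·r]; mITT = 2/[(1−f) + f·r].

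| r | FA, f = 10% / 20% | mITT, f = 10% / 20% |
|---|---|---|
| 1.00 | 1.90 / 1.80 | 2.00 / 2.00 |
| 0.75 | 1.92 / 1.84 | 2.05 / 2.11 |
| 0.50 | 1.95 / 1.89 | 2.11 / 2.22 |

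Neither set is closer to 2.0 throughout.

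**The case against.** Several objections carry weight.

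- **Primary does not mean only.** Protocol section 11 leaves details to a SAP, and the one supplied covers IDMC analyses. The main SAP may already include an FA table. This stands: the gap is in the protocol text, not proven in the whole plan.
- **mITT serves its stated target, seronegative children.** This stands. A reader might infer that FA should replace mITT for the between-arm comparison. The table in step 5 does not support that: at r = 0.75 or 1, mITT is nearer the naive ratio than FA.
- **Events in a dropped child do not vanish.** A reader might infer that they do, because RSV-positive cases leave the (S)AE analysis. But cases reported as (S)AEs stay in the database and are tabulated separately. That tabulation is specified under 11.7, and 11.1 bases all safety analyses on FA. Severe RSV-LRTI confirmed by the CEC goes to the IDMC with no mITT restriction (11.3.1.3, 11.9.1).
- **Nothing says the monitoring rule uses mITT.** Correct. The IDMC SAP defines only FA, and the halting power stated in 11.2 (at least 80% at about 25% versus 1%) comes out at 0.797 with all 18 per arm. Step 4 shows why the set should be named, not that the wrong one is in use.
- **A more dramatic example is available but unreliable.** At 18 per arm, 3 versus 0 gives a lower 95% limit of +0.003, so losing one case would seem to move the result out of the halt tier. But the example in 11.3.1.3 says 3 versus 0 does not clear the 95% limit. The protocol also records 37 enrolled, and 3/19 versus 0/18 gives −0.002. No weight is placed on it here.
- **The stakes are low.** Section 11.3.1 says the RSV endpoints are collected to assess feasibility and gain experience, and no hypothesis is tested. At the 1% control rate in 11.2, 18 × 0.01 = 0.18 severe control events are expected.

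**Conclusion.** The point holds as a minor one. The mITT exclusion depends on treatment, and the protocol states no FA counterpart for RSV infection although it does so for immunogenicity. A reader might go on to infer a bias against the vaccine, or in its favour. The documents support neither, because the sign depends on whether primed children have lower or higher risk than naive ones.

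The estimate of under one child per arm rests on assumptions: a 50% naive risk and a primed share of about 10% or less, or a modest risk difference if the share is larger. At a 20% share with no risk at all in primed children, the shift would reach 1.8 children. For the monitoring rule, the consequence is conditional on mITT being used and on an Ad26 case being a Day 8 responder.

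**What to change.** - **Protocol 11.1 and 11.6:** report RSV infection and severe RSV-LRTI by arm on the FA set beside mITT. Keep mITT as primary for the seronegative target, and state that its exclusion depends on treatment.
- **Protocol 11.3.1.3 and SAP 5.2:** name FA as the set for the monitoring rule, as the IDMC SAP already implies.
- If the main SAP already contains the FA table, a cross-reference in 11.6 is enough.

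The cost is a few sentences and one extra table, with no new data and no change to sample size. The drawback is that FA slightly dilutes an effect confined to naive children, which is why it sits beside mITT and does not replace it. Any replacements for Day 8 responders would also be in FA and should be flagged in that table.

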11.2. Sample Size Determination

The number of subjects chosen for this study will provide a preliminary safety and immunogenicity assessment. Control recipients (Nimenrix or placebo) are included for blinding and safety purposes and will provide additional control specimens for immunogenicity assays.

While mild to moderate vaccine reactions (local site and systemic responses) are expected, AEs that preclude further dose administration or more serious ones that would limit product development are not anticipated.

[Table 7](#) shows the probabilities of observing at least 1 AE at given true AE rates:

Table 7: Probability of Observing at Least One Adverse Event at a Given True Adverse Event Rate

True Adverse Event Rate	Probability of Observing at Least One Adverse Event in N Subjects	
	N=18	
0.5%	9%	
1%	17%	
2.5%	37%	
5%	60%	
10%	85%	
25%	99%	
50%	100%	

A monitoring rule for severe RSV-LRTI is described in Section 11.3.1.3. Based on this rule and assuming an event rate in controls of 1%, there is at least 80% power to halt enrollment in this or the next study if the incidence in the Ad26.RSV.preF group is approximately 25% or more.

11.3. Criteria for Endpoints of RSV Infection

11.3.1. Definitions for Endpoints of RSV Infection

The endpoints of RSV infection shown below will be collected to assess the feasibility of, and gain expertise in the collection of such events for future studies.

- Severe RSV-LRTI (secondary endpoint)
- RSV MA-RTI (exploratory endpoint)
- RSV-RTI (exploratory endpoint)
- RSV-LRTI (exploratory endpoint)

11.3.1.1. Definitions of Severe RSV-LRTI

Severe RSV-LRTI will be defined as the presence of severe LRTI as assessed by the CEC, and confirmation of RSV infection by nasal (mid-turbinate or nasopharyngeal) sample using independent RT-PCR by a central laboratory. See also Section 11.9.1. If no central laboratory RT-PCR result is available, a positive test result (including commercial test results) for RSV from a local laboratory (if available) could be used to confirm RSV infection upon evaluation by the CEC.

